For hemoglobin and the liver function enzyme (LFE) tests of ALT, AST, and alkaline phosphatase, the number and percentage of patients in each age/dose group with a maximum CTCAE Grade of 1, 2, 3, or 4 (as defined by the central laboratory and based on CTCAE v4.03) at any post-baseline visit (regardless of the baseline value) through the end of study will be summarized. All LFE tables will include summary rows for the number and percentage of patients with at least Grade 2 and at least Grade 3 laboratory abnormalities. The hemoglobin table will include a summary row for the number and percentage of patients with a Grade 3 laboratory abnormality. Accompanying listings of all ALT, AST, total serum bilirubin, direct bilirubin, and alkaline phosphatase will be created for any patients who had at least a Grade 3 ALT, AST, or alkaline phosphatase value. A listing of hematology results will be provided for patients with hemoglobin abnormalities.

The number and percentage of patients meeting the following criteria will be summarized overall and by dose and age group:

- ALT >3x ULN, ALT >5x ULN, ALT >10x ULN, ALT >20x ULN
- AST >3x ULN, AST >5x ULN, AST >10x ULN, AST >20x ULN
- ALT or AST >3x ULN, ALT or AST >5x ULN, ALT or AST >8x ULN, ALT or AST >10x ULN, ALT or AST >20x ULN
- Total bilirubin >2x ULN, Total bilirubin >3x ULN
- ALT or AST >3x ULN and Total bilirubin >2x ULN
- ALT or AST >3x ULN and Total bilirubin >2x ULN and Alkaline phosphatase  $\geq$ 2x ULN
- ALT or AST >3x ULN and Total bilirubin >2x ULN and Alkaline phosphatase <2x ULN

A patient or event will be counted if the post-baseline laboratory values meet the above criteria regardless of the baseline laboratory value (i.e., the post-baseline laboratory value does not need to be worse than the baseline laboratory value). For the last three combination categories, the values do not need to have been collected at the same assessment. For patients meeting any elevation criterion, a corresponding listing of all ALT, AST, alkaline phosphatase, and total, direct, and indirect bilirubin values will be provided.

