#### 11.4.3. Drug-Induced Liver Injury

Drug-induced liver injury (DILI) has been the most frequent single cause of safety-related drug marketing withdrawals and as such with this pediatric population (SMA patients) and unique intervention (gene therapy), the Sponsor took care to assess hepatic test results as drugs can cause liver injuries by many different mechanisms. Severe DILI cases rarely have been seen in drug development programs of significantly hepatotoxic drugs that do cause such injury. Evidence of hepatocellular injury is thus a necessary, but not sufficient, signal of the potential to cause severe DILI (note, however, that the drugs causing hepatic injury through mitochondrial toxicity may not cause early hepatotoxicity).

It is possible that although a drug may not cause severe liver injury, it could still result in laboratory evidence of mild, transient hepatic injury, with leakage of liver enzymes and the appearance in serum of elevations in aminotransferase activities to levels of 3, 5, and sometimes greater than 5 times the ULN. The liver enzyme data was evaluated according to these criteria and according to Hy's Law.

A finding of ALT elevation, usually substantial, seen concurrently with bilirubin  $> 2 \times \text{ULN}$ , identifies a drug likely to cause severe DILI (fatal or requiring transplant) at a rate roughly 1/10 the rate of Hy's Law cases. It is critical to rule out other causes of injury (e.g., other drugs or viral hepatitis) and to rule out an obstructive basis for the elevated bilirubin, so that alkaline phosphatase (ALP) should not be substantially elevated. In all cases to date, the small number of Hy's Law cases has arisen on a background of an increased incidence of more modest signs of hepatocellular injury (e.g., greater incidence of  $3 \times \text{ULN}$  elevations in ALT than seen in a control group).

Briefly, Hy's Law cases have the following three components:

- The drug causes hepatocellular injury, generally shown by a higher incidence of 3-fold or greater elevations above the ULN of ALT or AST than the (nonhepatotoxic) control drug or placebo.
- Among study patients showing such AT elevations, often with ATs much greater than  $3 \times \text{ULN}$ , one or more also show elevation of serum Total Bilirubin (TBL) to  $> 2 \times \text{ULN}$ , without initial findings of cholestasis (elevated serum ALP).

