- No other reason can be found to explain the combination of increased AT and TBL, such as viral hepatitis A, B, or C; preexisting or acute liver disease; or another drug capable of causing the observed injury.

A listing of patients meeting the ALT  $\geq 3 \times \text{ULN}$  and TBL  $\geq 2 \times \text{ULN}$  will be produced.

For patients enrolled in this study these criteria will be assessed in order to determine both general LFE changes according to change from baseline and over course of study. In addition, changes in ALT or AST relative to Total Bilirubin will be assessed to determine whether a signal related to DILI has occurred in any individual or group of patients.

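### As written, the ALP <2× ULN liver row excludes almost no one and overlaps the ALP ≥2× ULN row, because the values may come from different visits

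*SAP*

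**What the plan says.** SAP 11.4.2 ends its list of liver criteria with three combination rows. The first is ALT or AST >3× ULN with total bilirubin >2× ULN. The second adds ALP ≥2× ULN. The third is "ALT or AST >3x ULN and Total bilirubin >2x ULN and Alkaline phosphatase <2x ULN". Two counting rules follow. One concerns baseline: "A patient or event will be counted if the post-baseline laboratory values meet the above criteria regardless of the baseline laboratory value". The other concerns timing: "For the last three combination categories, the values do not need to have been collected at the same assessment". Neither says which of a child's ALP values decides between the second and third rows. The same paragraph then promises a listing of all ALT, AST, ALP and bilirubin values for any child who meets an elevation criterion.

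SAP 11.4.3 gives the reasoning behind such rows. It describes the signal as "A finding of ALT elevation, usually substantial, seen concurrently with bilirubin" above 2× ULN. It calls it critical "to rule out an obstructive basis for the elevated bilirubin, so that alkaline phosphatase (ALP) should not be substantially elevated". It also plans its own output, which begins "A listing of patients meeting the ALT" and uses ≥3× ULN for ALT and ≥2× ULN for bilirubin, with no AST alternative and no ALP condition.

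**The concern.** A waiver of same-visit pairing is a common, cautious choice when every criterion is an elevation, because it can only add children. ALP <2× ULN is a different kind of criterion. It is there to keep out children whose bilirubin rise may have a cholestatic basis. If any post-baseline value below the threshold satisfies it, a child with raised ALP at the time of injury qualifies through an ordinary result on another day.

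Liver safety is a focus of this trial. Protocol 5.5 names transient liver enzyme elevations as the event that appears to be associated with the product. Protocol 13.1.3 makes elevated liver enzymes an event of special interest. Protocol Appendix 3 ties Amendment 7 to an acute liver failure case. A reader of the safety table would take the two ALP rows as a split of the first row into two patterns, and as written they are not one.

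**Working it through.** The plan states no figure on this point, so the check applies the written rule.

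**Step 1: the rule as logic.** Let E mean that a child has at least one post-baseline ALT or AST >3× ULN and at least one bilirubin >2× ULN, at any visits.

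- Row without ALP: E.
- ALP ≥2× row: E, and at least one ALP ≥2× ULN (highest ALP ≥2×).
- ALP <2× row: E, and at least one ALP <2× ULN (lowest ALP <2×).

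A child in E is kept out of the <2× row only if every ALP is ≥2× ULN. A child with values on both sides of 2× ULN enters both rows, so the two rows can sum to more than the row they divide.

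**Step 2: number of ALP values.** ALP is on the chemistry panel at all visits (Protocol 12.14.2). From Protocol Tables 3 and 7:

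- Cohorts 1 and 2: Days 2, 7, 14, 21, 30, 60 (6) + Months 3 to 12 (10) = 16.
- Cohort 3: 16 + Day 44 + Day 72 + Month 15 = 19.

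**Step 3: chance that a child in E also enters the <2× row.** Assumption, not from the documents: draws are independent, each with probability q of ALP ≥2× ULN. The chance is 1 − qⁿ.

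| q | n = 16 | n = 19 |
|---|---|---|
| 0.5 | about 1.00 | about 1.00 |
| 0.8 | 1 − 0.028 = 0.97 | 1 − 0.014 = 0.99 |
| 0.9 | 1 − 0.185 = 0.81 | 1 − 0.135 = 0.86 |
| 0.95 | 1 − 0.440 = 0.56 | 1 − 0.377 = 0.62 |

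Independence is a simplification, since one child's values are correlated. Without it: if ALP is raised at 1 to 4 of 16 draws and the others are taken, 12 to 15 draws lie below 2× ULN and entry is certain.

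**Step 4: hypothetical children.** Each triplet is ALT, bilirubin, ALP in multiples of ULN at one draw.

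| Child | Draws | As written | ALP at the coinciding draw | Highest ALP |
|---|---|---|---|---|
| A, ALP raised at injury | (1, 0.5, 1) (6, 3, 3) (1, 0.5, 1) | both rows | ≥2× only | ≥2× only |
| B, ALP never ≥2× | (1, 0.5, 1) (6, 3, 1.2) (1, 0.5, 1) | <2× only | <2× only | <2× only |
| C, ALP raised at another visit | (1, 0.5, 1) (6, 3, 1.2) (1, 0.5, 2.5) | both rows | <2× only | ≥2× only |
| D, elevations never coincide | (6, 0.5, 1) (1, 3, 3) (1, 0.5, 1) | both rows | neither; needs a fallback | ≥2× only |

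The written rule gives A and C the same result although their ALP at the injury differs. Highest ALP makes the rows exclusive but files C by an unrelated visit.

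**Step 5: weight of one child.** 1/12 = 8% of a planned Dose B age group, 1/3 = 33% of Cohort 1, and 1/4 = 25% of the four children treated in Cohort 3 (SAP 2.2.1).

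**The case against.** The best defence is that the SAP never says any ALP below 2× ULN will do. A programmer could use the highest post-baseline ALP, which fits the waiver and makes the rows exclusive, and the mock-ups and programming notes are separate documents (SAP 16 and 18). This stands only in part. SAP 11.4.2 asks for a maximum in so many words when it summarises CTCAE grades, and it does not do so here. Highest ALP also misplaces child C.

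Several other points do stand:

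- SAP 11.4.2 does not call the <2× row a Hy's Law row; the link comes from 11.4.3, which is largely narrative and also requires other causes to be excluded. No summary row could settle a case.
- The row without ALP minus the ≥2× row gives the children whose ALP never reached 2× ULN, provided each has an ALP result. That is useful, though it is not ALP at the event.
- All liver values are listed for any child meeting an elevation criterion, and groups are small enough to read case by case.
- The error in the <2× row is one of over-inclusion. A child with ALP <2× ULN at the injury is never left out.
- SAP 13 says the SAP's safety analysis is not planned for the DSMB, so its interim safety reviews do not rest on this table.

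**Conclusion.** The point holds as a defect in two summary rows. Taken literally, the timing rule removes the ALP exclusion, makes the two rows overlap and leaves the <2× row close to a copy of the row without ALP. It also departs from the concurrence and absence of initial cholestasis described in 11.4.3. This rests on reading the waiver as it is worded, with no maximum or event-time ALP implied. The probabilities in the working rest on an assumed q and on independence. The percentages for one child apply only if a child meets both the ALT/AST and bilirubin criteria, and the documents give no rate for that.

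A reader might infer more, and the documents do not support it:

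- *That a false Hy's Law signal is likely.* Nothing in either document gives the chance of a qualifying child.
- *That the two patterns cannot be told apart at all.* The listing of all liver values and the subtraction above retain much of the information; only the printed counts mislead.
- *That the different criteria in the 11.4.3 listing lose children.* A child with raised AST alone is already in the all-values listing of 11.4.2. The difference between > and ≥ matters only for values exactly at the cut-off. This is a matter of tidiness.

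**What to change.** In SAP 11.4.2:

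1. Keep the any-time ALT/AST plus bilirubin row, and label it a screening count.
2. Classify the two ALP rows by the ALP value from the draw at which ALT or AST >3× ULN and bilirubin >2× ULN occur together. If several draws qualify, name the one to use, for example the first.
3. State a fallback for children whose elevations never coincide, for example ALP at the ALT/AST peak draw, and footnote those children. Child D would then go to the <2× row, although ALP was 3× ULN at the bilirubin rise.
4. State that the two ALP rows are mutually exclusive.

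Highest ALP, or ALP within a stated window of the elevations, would also be better than leaving the rule open. ALP at the coinciding draw is preferable because it is closest to 11.4.3.

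As a minor alignment, give the 11.4.3 listing the same ALT-or-AST criterion and the same cut-offs as the table.

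The cost is a few lines of SAP text and a small programming change. All four analytes are already on one panel, so no new data are needed.

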#### 11.4.3. Drug-Induced Liver Injury

Drug-induced liver injury (DILI) has been the most frequent single cause of safety-related drug marketing withdrawals and as such with this pediatric population (SMA patients) and unique intervention (gene therapy), the Sponsor took care to assess hepatic test results as drugs can cause liver injuries by many different mechanisms. Severe DILI cases rarely have been seen in drug development programs of significantly hepatotoxic drugs that do cause such injury. Evidence of hepatocellular injury is thus a necessary, but not sufficient, signal of the potential to cause severe DILI (note, however, that the drugs causing hepatic injury through mitochondrial toxicity may not cause early hepatotoxicity).

It is possible that although a drug may not cause severe liver injury, it could still result in laboratory evidence of mild, transient hepatic injury, with leakage of liver enzymes and the appearance in serum of elevations in aminotransferase activities to levels of 3, 5, and sometimes greater than 5 times the ULN. The liver enzyme data was evaluated according to these criteria and according to Hy's Law.

A finding of ALT elevation, usually substantial, seen concurrently with bilirubin  $> 2 \times \text{ULN}$ , identifies a drug likely to cause severe DILI (fatal or requiring transplant) at a rate roughly 1/10 the rate of Hy's Law cases. It is critical to rule out other causes of injury (e.g., other drugs or viral hepatitis) and to rule out an obstructive basis for the elevated bilirubin, so that alkaline phosphatase (ALP) should not be substantially elevated. In all cases to date, the small number of Hy's Law cases has arisen on a background of an increased incidence of more modest signs of hepatocellular injury (e.g., greater incidence of  $3 \times \text{ULN}$  elevations in ALT than seen in a control group).

Briefly, Hy's Law cases have the following three components:

- The drug causes hepatocellular injury, generally shown by a higher incidence of 3-fold or greater elevations above the ULN of ALT or AST than the (nonhepatotoxic) control drug or placebo.
- Among study patients showing such AT elevations, often with ATs much greater than  $3 \times \text{ULN}$ , one or more also show elevation of serum Total Bilirubin (TBL) to  $> 2 \times \text{ULN}$ , without initial findings of cholestasis (elevated serum ALP).
- No other reason can be found to explain the combination of increased AT and TBL, such as viral hepatitis A, B, or C; preexisting or acute liver disease; or another drug capable of causing the observed injury.

A listing of patients meeting the ALT  $\geq 3 \times \text{ULN}$  and TBL  $\geq 2 \times \text{ULN}$  will be produced.

For patients enrolled in this study these criteria will be assessed in order to determine both general LFE changes according to change from baseline and over course of study. In addition, changes in ALT or AST relative to Total Bilirubin will be assessed to determine whether a signal related to DILI has occurred in any individual or group of patients.

## 11.5. Vital Signs

Vital signs will include blood pressure, respiratory rate, pulse, heart rate, pulse oximetry and axillary temperature. Body weight and length and/or height will also be collected.

Vital signs will be examined at each scheduled visit and time point. The baseline value will be the last measurement before date and time of the injection of study drug. Mean changes from baseline to each post-baseline visit and time point will be summarized with the baseline mean, visit/time point mean, change from baseline mean, standard deviation, minimum, maximum, and median. Summaries will be presented overall and by actual dose received and age group.

In addition, vital signs results will be flagged as PCS if they meet the pre-specified criteria which are defined outside of this SAP. The number and percent of patients meeting each PCS criterion at each scheduled visit and time point will be summarized overall and by actual dose received and age group. For body weight, the PCS criteria are based on percentile weights for age and sex as defined by the World Health Organization Child Growth Standards. These definitions extend

through 60 months of age. If a patient is >60 months of age at the time of their weight assessment, they will not be assessed for PCS weight values.

## 11.6. ECG

A 12-lead ECG will be conducted at scheduled visits of Screening/Baseline, Day 1, Day 2, Day 3, Month 3, Month 6, Month 9, and Month 12 (or Early Termination), and assessed by a central reviewer. The baseline value will be the last measurement on or before the day of injection of study drug. Mean changes from baseline, standard deviation, minimum, maximum, and median to End of Study/Early Termination visit will be summarized for HR, PR, QR, QRS, QTcF as measured by the central reviewer.

The central reviewer will identify abnormal ECGs that are PCS, the definitions for which are maintained outside of this document.

A listing of all PCS ECGs will be provided. Summaries of ECG data will be presented overall and by actual dose received and age group.

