## 12.7. Electrocardiogram

A 12-lead electrocardiogram (ECG) will be performed as specified in the SoA ([Table 3](#)). For patients enrolled in the study prior to Amendment 5 and irrespective of study schedule, after signing an updated informed consent, all patients should have a 12-lead ECG at their next scheduled visit and then in conformity with the SoA ([Table 3](#)).

The ECG will be interpreted locally by a cardiologist or designee for immediate safety evaluation. The ECG tracings or ECG machine data will also be collected for centralized review and interpretation by a cardiologist.

A 12-Lead ECG will be performed (concurrent with Holter Monitor) as specified in the SoA ([Table 3](#)). Additional electrophysiological monitoring will be at the discretion of the Investigator as per local institutional guidelines.

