#### **4.8.1.4. Electrocardiogram (ECG)**

Standard 12-lead ECGs will be performed at screening/baseline, Day 1, Day 2, Day 3, Month 3, Month 6, Month 9, Month 12, and Month 15 (Cohort 3 only) visits (or Early Termination) including heart rate, PR, QRS, QTcF. 12-lead ECG will also have QR included. 12-lead ECG tracings will be interpreted locally; however, the tracings will be submitted to a centralized interpreter for inclusion in the study dataset. Only descriptive statistics are planned for this data.

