### 6.2. Key Definitions

#### 6.2.1. Baseline Values

Unless otherwise specified, the baseline values of safety parameters and efficacy parameters of the patients enrolled in the study are defined as the last non-missing measurement or assessment prior to the dose of study medication. If multiple measurements are recorded on the same day, the last measurement recorded prior to the dose of study medication will be used as the baseline value. If these multiple measurements occur at the same time or time is not available, then the average of these measurements (for continuous data) or the worst among these measurements (for categorical data) will be considered as the baseline value.

For patients  $\geq$  6 months and  $<$  24 months at time of dosing who continue in study past 24 months of age, the score and change from baseline of HFMSE will also be the calculated. The baseline HFMSE will be defined as the patients’ first measurement of HFMSE after passing 24 months of age.

The baseline values of parameters of patients from the PNCR are defined as those captured for the study-defined baseline visit. In cases where the baseline visit HFMSE assessment was not completed, the baseline value will be defined as the first non-missing assessment.

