#### **6.2.2. Study Day**

For patients enrolled in the study, the only dose of study medication will be administered on study day 1. The study day for an event occurring on or after the dose date is defined as event date – dose date + 1. The study day for an event occurring prior to the dose date is defined as event date – dose date.

For patients from the PNCR dataset, the date of baseline assessment for the primary endpoint will be considered study day 1. The study day for an event occurring on or after the date of enrollment is defined as event date – enrollment date + 1. The study day for an event occurring prior to the date of enrollment is defined as event date – enrollment date.

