**Table 4.2: Analysis Time Windows of Bayley Scales, HFMSE, Development Milestones and Pulmonary Exam – Cohort 3 Patients**

Scheduled Visit	Nominal Days (Study Day)	Acceptable Analysis Window in Study Days (Min Day – Max Day)
Baseline	-	< 1
Month 1	30	1 to 38
Day 44	44	39 to 49
Month 2	60	50 to 66
Day 72	72	67 to 77
Month 3	90	78 to 104
Month 4	120	105 to 134
Month 5	150	135 to 164
Month 6	180	165 to 194
Month 7	210	195 to 224
Month 8	240	225 to 254
Month 9	270	255 to 284
Month 10	300	285 to 314
Month 11	330	315 to 344
Month 12	360	345 to 374

Scheduled Visit	Nominal Days (Study Day)	Acceptable Analysis Window in Study Days (Min Day – Max Day)
Month 13	390	375 to 404
Month 14	420	405 to 434
Month 15	450	≥435

Safety data, such as laboratory results, vital signs, ECGs, and physical exams will be assessed by date and study day. For change from baseline analyses the value associated with the scheduled visit will be used. For summaries of shifts from baseline and potentially significant values all values will be considered for these analyses. Baseline for safety measures will be defined as the latest value before Day 1.

The efficacy data of this study will be compared to the data from the PNCR network. The analysis visit of PNCR will be based on the visit month defined in the PNCR dataset.

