### 11.4.2. Statistical Methods

Clinical laboratory tests at each scheduled visit will be summarized overall and by actual dose received and age group. The baseline value will be the last measurement on or before the day of the injection of study product. Mean changes from baseline to each post-baseline visit will be summarized for each protocol-specified hematology, clinical chemistry, coagulation, and capillary blood gas laboratory parameter with the baseline mean, visit mean, change from baseline mean, standard deviation, minimum, maximum, and median.

Immunology and virus serology data will be summarized using descriptive statistics appropriate for categorical variables (i.e. number and percentage of patients with each reported result at each visit). Urinalysis data will only be presented in listings.

Chemistry, hematology, and coagulation laboratory data values will be categorized as low, normal, or high based on normal ranges of the laboratory used in this study. Shift tables from baseline to minimum value, maximum value, and final treatment values will be created. The shift tables will cross tabulate the frequency of patients with baseline values below/within/above the normal range versus minimum/maximum/final values below/within/above the normal range.

The number and percentage of patients with post-baseline values meeting the specified criteria for PCS laboratory values will be summarized overall and by actual dose received and age group. A post-baseline value must be more extreme than the baseline value to be considered a PCS finding. A listing will be provided to present the entire set of lab values for a patient for the parameter meeting PCS criteria during treatment.

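### SAP 11.6 and SAP 6.5 define the ECG baseline differently, and 11.6 would also admit a post-dose Day 1 ECG

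*SAP*

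**What the plan says.** The SAP gives a safety baseline in several places.

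- **ECG (SAP 11.6):** "The baseline value will be the last measurement on or before the day of injection of study drug". The rule works at the level of the calendar day, with no clock-time condition.
- **Laboratory (SAP 11.4.2):** almost the same wording, "The baseline value will be the last measurement on or before the day of the injection of study product".
- **All safety measures (SAP 6.5, paragraph after Table 4.2):** "Baseline for safety measures will be defined as the latest value before Day 1". The paragraph lists laboratory results and ECGs by name and makes no exception for later sections.
- **General definition (SAP 6.2.1, and similarly 1.1):** "the last non-missing measurement or assessment prior to the dose of study medication". Both are defaults that give way where another section specifies something else.
- **Vital signs (SAP 11.5):** the last measurement before the date and time of injection.

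On timing, SAP 6.2.2 says that "the only dose of study medication will be administered on study day 1". SAP 11.6 schedules the ECG for that same day: "A 12-lead ECG will be conducted at scheduled visits of Screening/Baseline, Day 1, Day 2, Day 3". SAP 4.8.1.4 agrees: "Standard 12-lead ECGs will be performed at screening/baseline, Day 1, Day 2, Day 3". Protocol 12.7 adds only that "A 12-Lead ECG will be performed (concurrent with Holter Monitor) as specified in the SoA". The schedule of assessments marks a 12-lead ECG at screening, Day 1 and Days 2-3, and leaves Day -1 blank.

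**The concern.** A programmer deriving the ECG baseline has two instructions that cannot both be followed. Independent double programming (SAP 17) does not help, because both programmers work from the same contradictory text.

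The second problem is what 11.6 permits. A baseline should be free of treatment effect. A rule that stops at the calendar day of dosing does not ensure this when a measurement is scheduled that day and its position relative to the injection is not given. If the Day 1 tracing follows the injection, every later ECG is compared with a value that may already carry an effect of the product or the procedure.

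Cardiac safety is of interest in this programme. The protocol (5.3 and 5.5) reports heart findings in mice whose relevance to primates is unknown, and SAP 11.3.2.4 lists cardiac events among the adverse events of special interest.

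**Working it through.** No figure in the plan depends on this point, so the check applies each rule to the plan's own schedule and sees which measurement it selects.

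**Inputs.** Dosing is on Day 1 (SAP 6.2.2). Scheduled 12-lead ECGs around dosing are at screening (Day -60 to -2), Day 1 and Days 2-3 (schedule of assessments). Routine blood draws are at screening, Day -1 and Day 2, with none on Day 1 (schedule; Protocol 12.14 and Table 7).

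**ECG baseline selected from scheduled tracings**

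| Rule | Day 1 ECG before dosing | Day 1 ECG after dosing |
|---|---|---|
| SAP 11.6 | Day 1 | Day 1 (post-dose) |
| SAP 6.5 | Screening | Screening |
| SAP 1.1 / 6.2.1 (defaults) | Day 1 | Screening |

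The rows for 11.6 and 6.5 differ in both columns, so the conflict exists whatever the timing. Section 11.6 departs from the defaults only in the right-hand column.

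**Which column applies?** SAP 4.8.1.4, SAP 11.6, Protocol 12.7 and the schedule do not say. The protocol does fix the timing of another Day 1 item: section 12.13 places the injection-site photograph before the injection. It has no such statement for the ECG.

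**How many rules truly conflict with 11.6?** Sections 1.1 and 6.2.1 yield to a more specific section, so 11.6 overrides them. Section 11.5 governs vital signs only. That leaves one direct contradiction, 6.5.

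**Direction of bias if the baseline is post-dose.** Let *a* be the shift already present in the Day 1 tracing and *e* the true shift at the end-of-study visit, both relative to the pre-dose value.

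Reported change = (pre-dose + *e*) − (pre-dose + *a*) = *e* − *a*, so the bias is −*a*.

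- If the acute shift persists unchanged (*e* = *a*), the reported change is 0 and a real effect disappears.
- If it resolves (*e* = 0), the reported change is −*a*, a spurious change of opposite sign.

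The documents give no value for *a* or *e*, so the size cannot be computed.

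**Laboratory baseline.** For scheduled samples every rule selects Day -1, or screening for tests not drawn on Day -1. The rules part only if an unscheduled same-day sample exists, which Protocol 12.14.1, 12.14.2 and 12.14.5 allow at the investigator's discretion. Such a sample could alter a potentially-clinically-significant flag, because SAP 11.4.2 requires the later value to be more extreme than baseline.

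**The case against.** The best defence is that little depends on this. SAP 11.7 extracts triplicate ECGs from the Holter at a labelled pre-dose point and at eight times from 2 to 48 hours. It summarises HR, PR, QRS and QTcF at each time and counts potentially clinically significant findings from 2 to 48 hours. The 11.6 baseline does not enter those summaries. What 11.6 reports is a descriptive change to the end-of-study or early-termination visit. Its listing of abnormal ECGs relies on the central reviewer's criteria, held outside the SAP, and nothing shown ties them to this baseline. If the Day 1 ECG is pre-dose, 11.6 is arguably the better rule, because it uses a same-day value where 6.5 goes back to a tracing up to 60 days old.

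Most of this stands, and it limits the point to a minor one. It does not remove the contradiction with 6.5. Nor does the Holter section fully replace 11.6, since it defines no baseline, states no change-from-baseline summary and omits QR.

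A reader might infer more than the documents support:

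- **That 11.6 conflicts with every other baseline rule.** Only 6.5 conflicts directly.
- **That the Day 1 ECG is taken after dosing or under sedation.** Protocol 10.6 requires sedation for the procedure but does not link it to the ECG, and the timing is left open.
- **That the bias runs towards no change.** That needs an acute effect that persists to the later visit.
- **That laboratory results are broadly affected.** Scheduled samples are not.

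**Conclusion.** The point holds as a contradiction between two stated rules, together with a timing gap. For any patient with a Day 1 12-lead ECG, SAP 11.6 and SAP 6.5 select different baselines, and 11.6 would accept a post-dose tracing. The first part follows from the text and the schedule alone. The second matters in practice only if some Day 1 ECGs were taken after the injection, which the documents neither state nor exclude.

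Severity is minor. The affected output is the descriptive change from baseline in HR, PR, QR, QRS and QTcF. No primary endpoint, hypothesis test, sample size or significance level is involved. The bias could go either way and its size is unknown. The laboratory wording matters only for unscheduled same-day tests.

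**What to change.** 1. In SAP 6.5, 11.4.2 and 11.6, adopt the rule already used in 11.5: the last non-missing value before the date and time of injection.
2. State in the ECG section and the schedule whether the Day 1 12-lead ECG is taken before or after dosing.
3. For a Day 1 value with no recorded time, use it as baseline only if it is documented as pre-dose. Otherwise use the last value before Day 1. This avoids discarding a genuine pre-dose tracing in favour of an older screening one.
4. Align item 3 with SAP 6.2.1, which averages several same-day continuous measurements, or takes the worst categorical one, when times are equal or missing. Averaging should cover only values known to be pre-dose.

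The cost is a few lines of SAP wording and one baseline derivation. No new data are needed.
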